NCT 03632447

A Prospective Randomized Efficacy Study Comparing a Pelvic Digital Health System Home Program of Pelvic Floor Muscle Exercise to Kegel Exercises in the Treatment of Stress-Predominant Urinary Incontinence

Statistical Analysis Plan

August 27, 2019

Statistical Analysis Plan

Secondary analysis of a Prospective, Nested, Randomized Efficacy Study Comparing a Pelvic Digital Health System Home Program of Pelvic Floor Muscle Exercise to Kegel Exercises in the Treatment of Stress-Predominant Urinary Incontinence (Renovia-05) –
Pilot/Feasibility Trail

Principal Investigator: Renovia Inc.

Prepared by: [name]

August 12, 2019

Table of Contents

1. Objectives.....	3
2. Design.....	3
3. Statistical analysis	3
3.1 Participant description.....	3
3.2 Feasibility	3
3.2.1 Feasibility of randomization.....	3
3.2.2. Feasibility of digital health platform	3
3.3 Compliance	4
3.4 8-week assessment	4
3.5 General statistical analysis guidelines.....	5
4. Additional comments.....	6
4.1 Reporting of statistical analyses	6
4.2 Additional analyses	6

1. Objectives

- Assess the feasibility of a randomized trial to test the efficacy of using a novel intravaginal system (leva[®] Plus Pelvic Digital Health System) to perform pelvic floor muscle exercises (PFME) compared to a Kegel exercise home program in women with stress-predominant urinary incontinence (SUI)
- Assess any technical issues with the digital aspect of the leva[®] Plus Pelvic Digital Health System
- Evaluate compliance with exercises in the leva[®] Plus Pelvic Digital Health System arm of the study

2. Design

The initial randomized study was ended early due to technical difficulties. This will be analyzed as a pilot/feasibility trial. Details about the randomized controlled trial study design and study visits can be found in the protocol, Renovia-05 (Sponsor: Renovia Inc.)

The study enrolled 60 women, randomized into the two initial arms (30 women per arm) and followed participants for 8 weeks.

3. Statistical analysis

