3.5 General statistical analysis guidelines

The analyses will be conducted in the entire population. The denominator for all data will be the total number of women randomized to each group. Two-sided p-values less than 0.05 will be considered statistically significant.

Normality of continuous variables will be assessed using the Shapiro-Wilkes test and a visual inspection of the data distribution. Continuous variables that are normally distributed will be reported as means \pm standard deviation. Non-normally distributed data will be reported as median and interquartile range (25th and 75th percentile). Categorical variables may be collapsed as necessary depending on data distribution, although all efforts will be made to maintain pre-determined categories. Categorical variables will be presented as n (%).

Data will be examined descriptively. Crude proportions of the primary and secondary outcomes at 8 weeks will be reported. Log-binomial regression will be used to calculate risk ratios and 95% confidence intervals (CIs) to assess whether the intervention was efficacious. We will assess each portion of efficacy separately (improvement and distress) as well as combined. If differences between the intervention and control groups as seen as baseline, these may be adjusted for in a log-binomial regression.

Chi-square or Fisher's exact tests may be used to calculate p-values to assess differences between categorical variables, as appropriate based on distribution of the data. To assess differences in normally distributed continuous variables between groups, the Student's T-test will be used to calculate p-values. To assess differences in non-normally distributed continuous variables between groups, the Wilcoxon rank-sum test will be used. Log-binomial regression will be used to calculate risk ratios and 95% CIs to assess the association between the intervention and all categorical variables. Linear regression will be used to calculate difference in means and 95% CI to assess the relationship between the intervention and all continuous variables.

In the event that the log-binomial regression does not converge, modified Poisson regression with robust standard errors will be substituted. If this is consistent problem, the statistician may decide to use this approach for all calculations of risk ratios and 95% CIs.

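### For a continuous outcome judged non-normal, the SAP pairs a rank-sum p-value with a mean-difference interval, and no stated continuous analysis uses the outcome's baseline value

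*SAP*

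**What the plan says.** All of this is in SAP section 3.5, General statistical analysis guidelines.

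- **Choice of test.** "Normality of continuous variables will be assessed using the Shapiro-Wilkes test and a visual inspection of the data distribution". No threshold is given, and no rule for when the test and the visual impression differ.
- **P-value, continuous outcomes.** Student's t-test if judged normal. Otherwise: "To assess differences in non-normally distributed continuous variables between groups, the Wilcoxon rank-sum test will be used".
- **Estimate and interval, continuous outcomes.** "Linear regression will be used to calculate difference in means and 95% CI to assess the relationship between the intervention and all continuous variables". Non-normal variables are not excepted, although they are summarised by median and quartiles.
- **Binary outcomes.** Log-binomial regression gives the risk ratio and interval for efficacy, with modified Poisson as the fallback. For p-values, chi-square or Fisher's "exact tests may be used to calculate p-values".
- **Significance.** "Two-sided p-values less than 0.05 will be considered statistically significant".
- **Baseline.** The only adjustment mentioned is optional: a log-binomial model may adjust for baseline differences if they are seen. Yet the flow chart in Protocol section 4, the baseline visit in Protocol section 8.1 and SAP section 3.1 show that PFDI, PFIQ, SESPPFE, WHODAS, PISQ-IR and PFDx are all collected at baseline.

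**The concern.** A skewed questionnaire score would be summarised by its median, tested on ranks and estimated as a difference in means. A rank-sum test asks whether values in one arm tend to exceed those in the other. The regression interval concerns the means. With skewed data, one can favour a difference while the other does not, and the SAP has no rule for reporting that case. Which test applies is also settled after looking at the outcome data, partly by eye.

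This reaches many 8-week results in SAP section 3.4: the questionnaire scores, the PFDx measures and the Brink score. Pelvic floor muscle performance, which PFDx measures, is listed among the primary objectives in Protocol section 7.1. A pilot's estimates and intervals are what a later trial would draw on, so they should match the test printed beside them.

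Omitting the baseline value is a separate loss in the same paragraph. With 60 women, any precision available from data already collected is worth having.

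**Working it through.** **Inputs from the documents.** 30 women per arm (SAP section 2); two-sided 0.05 (SAP section 3.5); 30% success in controls and a 20-point difference (Protocol section 10.1.1). The documents give no standard deviations, distribution shapes or baseline correlations, so those below are assumptions.

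**The plan's own figure.** With pooled variance under the null and mean rate 0.40:

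n = [1.960 × √(2 × 0.4 × 0.6) + 0.842 × √(0.3 × 0.7 + 0.5 × 0.5)]² / 0.20² = (1.358 + 0.571)² / 0.04 ≈ 93 per arm.

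This matches Protocol section 10.1.1 and is not in dispute; it supplies the 30% v 50% used below.

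**Continuous outcomes.** 20,000 simulated trials per setting, 30 per arm. Shapiro-Wilk p < 0.05 in either arm sends the outcome to rank-sum. A conflict means that the p-value and the regression interval give opposite verdicts.

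| Assumed data | Sent to rank-sum | Conflict among those sent |
|---|---|---|
| Log-normal, σ = 1, no effect | 100% | 4.7% |
| Log-normal, σ = 1, 1.65-fold shift | 100% | 20.9% |
| Log-normal, σ = 0.6, no effect | 97.5% | 3.6% |
| Log-normal, σ = 0.6, 1.4-fold shift | 97.5% | 14.8% |
| Normal, no effect | 9.5% | 3.4% |
| Normal, 0.5 SD effect | 9.9% | 11.7% |

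For normal data the overall rate is therefore 0.095 × 0.034 = 0.3% with no effect and 0.099 × 0.117 = 1.2% with an effect. In the 20.9% row, 16.2 points are a significant rank-sum test with an interval that includes zero, and 4.7 points are the reverse.

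Further runs of 3,000 to 6,000 trials per setting, with the same rule, show how far the rate depends on shape:

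- exponential or log-normal data shifted by 0.5-0.7 SD: 17-36%
- exponential data with a change of scale: about 15%
- bounded beta-shaped scores with an effect: 4-13%
- a six-item 0-4 score rescaled to 0-100, with mild to heavy floor and an effect: 2-9%
- no effect: 1-5%

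The two-stage type I error was 4.9-5.2%. In the t-test branch the conflict rate was 0%, because the unadjusted regression and the t-test are the same test. Taking p-value and interval from the same regression gave 0 conflicts in 20,000 trials in every setting.

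**Binary outcomes.** All 30 v 30 tables were enumerated, with the interval from the Wald log risk ratio.

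- At 50% v 30%: chi-square conflicts with the interval in 0.5% of trials, Fisher in 8.7%.
- At 30% v 10%: chi-square 13.2%, Fisher 7.4%. Part of this comes from tables with no control successes (probability 0.9³⁰ = 4.2%), where the ratio cannot be estimated and was counted as not excluding 1. Depending on the rates, the test and how such tables are treated, low success rates give roughly 3-13%.

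Example, 16/30 v 8/30: the risk ratio is 2.00 and its log has SE √(1/16 − 1/30 + 1/8 − 1/30) = 0.348. The 95% interval is exp(0.693 ± 1.96 × 0.348) = 1.01 to 3.95. Chi-square p = 0.035; Fisher p = 0.064.

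**Baseline adjustment.** The variance factor is 1 − r². At r = 0.4 it is 0.84, a 16% cut, worth 30/0.84 ≈ 36 women per arm. At r = 0.6 it is 0.64, a 36% cut, worth 30/0.64 ≈ 47 per arm.

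**The case against.** The strongest reply is that the SAP largely assigns roles. Significance is tied to the p-value, the continuous p-value source is named, and log-binomial regression is the stated tool for judging efficacy, with chi-square and Fisher only optional. A reader might infer that either result may be quoted at will. The text does not support that. What is missing is narrower: a rule for when the two disagree, and an interval that matches the rank-sum test.

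A reader might also infer that the normality check governs the primary results. It does not, because SAP section 3.4 makes both primary outcomes dichotomous. Their only possible mismatch is between an optional test and the log-binomial interval. At 50% v 30% the expected counts are 12 and 18, so chi-square is the usual choice and the 0.5% figure applies rather than Fisher's 8.7%.

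The high conflict rates also need care. PFDI and PFIQ scales run from 0 to 100, and a pure shift of an unbounded skewed distribution is not a natural model for them. The lower range for bounded scores is the fairer guide there.

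On baseline, the correlation is assumed, and the UDI-6 entry threshold of 25 narrows the baseline range and may lower it for the urinary score. That tempers the size of the gain, but not the case for using the data.

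Finally, this is a pilot whose objectives are feasibility, technical issues and compliance, and the SAP itself asks for caution in reporting. That limits the consequence. It does not tell a reader what to make of a test and an interval that differ.

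**Conclusion.** The point holds for continuous 8-week outcomes judged non-normal. There the p-value and interval address different quantities, whatever distribution is assumed. How often they conflict does depend on the assumed shape: with a true effect, about 15-36% for strongly skewed unbounded data and 2-13% for bounded scores; with no effect, about 1-5%.

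A reader might infer that choosing the test from the data inflates false positives. The simulated type I error of 4.9-5.2% does not bear that out; the harm is inconsistent reporting and a target quantity that depends on the data. For the binary primary outcomes the problem is small at the protocol's design rates and becomes noticeable only if success rates are low or Fisher's test is used.

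The missing baseline adjustment is a real but modest loss, 16-36% of variance if the correlation is 0.4-0.6. Overall this should be corrected before analysis, but it does not undermine the study.

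**What to change.** In SAP section 3.5:

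1. For between-arm comparisons of continuous 8-week outcomes measured at baseline, drop the normality check. Take estimate, 95% interval and p-value from one linear regression on arm and the outcome's baseline value, with robust standard errors.
2. If rank-sum is wanted for particular measures, name them in the SAP before analysis, so that the data do not choose the method again, and report the Hodges-Lehmann shift with its interval. That pairing should agree with the test apart from ties; it was not simulated here.
3. For the binary efficacy outcomes, take p-value and interval from the same log-binomial model, or from the modified Poisson model where that is substituted.

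Medians and quartiles can stay as descriptive summaries. The cost is a few sentences of SAP text and small changes to code. The downside is some loss of power against rank-sum for very skewed outcomes, which item 2 lets the authors avoid for measures they can identify in advance.

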4 STUDY EVENTS FLOW CHART

Intervention and outcomes	Screening Visit	Baseline	4 weeks	8 weeks	6 months	12 months
Eligibility and informed consent	x					
Urine Pregnancy Test (if indicated)	x					
UDI-6	x					
Medical History	x	*				
MESA questionnaire	x					
POP-Q	x [#]			x		
Brinks Scale		x [*]		x		
Primary Outcome Measures (PFDI, PGI-I, PGI-S)		x	x	x	x	X
PFDI, WHODAS, PISQ-IR, McGill Pain Questionnaire, SESPPFE, PGI-S, PGI-I, PFIQ		x	x	x	x	X
PFM performance assessment (PFDx)		x	x	x		
3-day voiding diary	x (before baseline visit)			x		
CGI-S, CGI-I	x			x		
Complications			x	x		
Follow up questions detailing further treatments for SUI					x	X

*May be done at screening visit if < 3 months prior to baseline visit

May be from a visit within 3 months of baseline visit.

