7 STUDY OBJECTIVE AND ENDPOINT

7.1 Study Objective

Primary objectives:

- Compare the efficacy of using an innovative intravaginal system (leva® Digital Pelvic System™) to perform pelvic floor muscle exercises (PFME) compared to a Kegel exercise home program in women with stress-predominant urinary incontinence (SUI).
HYPOTHESIS: The leva® Plus Pelvic Digital Health System is superior to a home PFME program in the treatment of stress-predominant urinary incontinence.
- Compare the effect of the Leva® Plus Pelvic Digital Health System with home PFME program on measures of pelvic floor muscle performance
HYPOTHESIS: The leva® Plus Digital Pelvic System leads to more significant improvements in pelvic floor muscle performance than a home PFME program
- Evaluate the contribution of the Digital Health Platform in adherence and treatment of SUI for long term maintenance therapy.
HYPOTHESIS: The Digital Health Platform improves adherence to a long-term maintenance program of pelvic floor muscle exercises.

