Subjects will complete validated standardized quality of life questionnaires and pelvic floor muscle testing using the PFDx device at in-office visits at baseline, 4 weeks and 8- weeks. They will record 3-day voiding diaries at baseline and at 8-weeks. Beyond 8- weeks subjects will be asked to participate in follow-up calls at 6 and 12 months and complete validated standardized quality of life questionnaires by mail or email. Patients who were randomized to the Leva arm of the study and were sub-randomized to the “follow up reminder” will receive weekly reminders to perform their pelvic floor exercises using the Leva device

The study will be funded by Renovia, who will provide leva Plus and PFDX devices for the study and subject re-numeration.

\$50 for the baseline visit with the study team
\$50 for the 4-week follow up visit
\$100 for the 8-week final study visit
\$50 for the completion of >80% of the study exercises
\$50 upon completion and return of surveys at 6 months
\$50 upon completion and return of surveys at 12 months.

Please note that \$300 compensation is provided for every subject who completes the study in its entirety. This compensation level will increase to \$350 for those subjects in either arm who attest to completion of >80% of the study exercises.

Initial payment will occur by the site and in a manner consistent with individual site policy after the completion of the 8-week final study visit. Compensation will occur immediately following the return of completed 6-month and 12-month surveys.

If the subject leaves study early, the subject will receive a pro-rated amount based on the study milestones completed. Subjects will be compensated \$25 for unscheduled return visits.

Subjects will be reimbursed for parking costs associated with their visits.

Visit #1 – Baseline visit - the participants will undergo the following procedures:

Following completion of baseline evaluation and consent, patients will be randomized by study coordinators at the baseline office visit using an automated randomization system.

- 1) Medical history including GYN history, OB history, medical diagnoses, medications, and prior surgical procedures.
- 2) Questionnaires:
 - a. PFDI
 - b. PISQ-IR
 - c. McGill Pain Questionnaire
 - d. SESPPFE
 - e. Patient Global Impression of Severity (PGI-S) Scale
 - f. WHODAS

- g. PFIQ
- 3) Voiding diary – collection of a 3-day intake and output and symptoms diary completed *before* baseline visit

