 - 4) Health Care Provider will perform a Pelvic Organ Prolapse Quantitative (POP-Q) assessment (If not completed at screening)
 - 5) The PFDx device will be then used to measure the pelvic floor angles and strength. This will be supervised by clinical research personnel blinded to randomization.
 - 6) To optimize blinding to arm, the randomization will occur following the above surveys and evaluations.

Following randomization, the subject will participate in one of two main study arms:

KEGEL STUDY ARM

- Subjects randomized to the Kegel Arm will receive standardized written and verbal instructions on how to perform three times daily/7 days per week pelvic floor muscle exercises and their ability to perform the correct muscle action will be confirmed by physical exam (written instructions per the handout, adapted from Voices for PFD). They will be instructed to perform these exercises three times daily throughout the 8-week study period, based on a commonly used kegel regimen. These instructions will occur during the baseline visit. Also at the baseline visit, subjects will be informed they will be asked to attest to the fact that they performed these exercises twice daily at least 80% of the time (approximately 17 times per week). This attestation will ask the subject to recall their adherence; no diary or other record will be required.
- Subjects will return to the office on week 4 to participate in validated questionnaires and undergo a progress evaluation using the PFDx. For clinical questions they will be directed to follow up with their physician. Their evaluator will be blinded to their randomization.
- Subjects will return to the office on week 8- to participate in validated questionnaires, undergo progress evaluation using the PFDx, and physical examination including a POP-Q and Brinks score, and attest to their adherence. Their evaluator will be blinded to their randomization
- Following week 8, patients will be recommended to continue weekly Kegel exercises, but will be free to pursue alternative treatments if desired. They will participate over the phone and via email or mail in validated questionnaires, in addition to reporting what (if any) additional therapies they have undergone for treatment of stress urinary incontinence at 6 months and 12 months after baseline.

LEVA STUDY ARM

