10.1.1 Determination of Sample Size

This planned randomized controlled trial is a tertiary prevention trial, comparing the efficacy of the Leva device in the treatment of stress urinary incontinence to standard pelvic floor muscle training, consisting of office education and a home exercise program. Our primary outcome is the proportion of subjects who are very much better/much better as measured by the PGI-I. Sample size for 20% difference between groups given a 30% success rate of home exercise programs, $\alpha=0.05$, and a power of 0.8, the needed sample size is 93 patients in each arm. Allowing for an attrition rate of approximately 15%, we require approximately 225 patients.

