- **Pelvic Floor Impact Questionnaire (PFIQ):** Obtain the mean value for all of the answered items within the corresponding scale (possible value 0 – 3) and then multiply by (100/3) to obtain the scale score (range 0-100). Missing items are dealt with by using the mean from answered items only. To obtain a summary score, add the scores from the 3 scales together (range 0-300). This can be reported as a continuous variable or may be categorized depending on distribution of the data.
- **Pelvic Organ Prolapse assessment (POP-Q):** Assessment of pelvic organ prolapse will be conducted as medically directed. POP-Q stages may be reported as 0-IV, dichotomized as greater than or equal to Stage II vs. less than Stage II, or categorized depending on distribution of the data.
- **PFDx:** Assessment of baseline angle (rest angle), maximum angle (maximum squeeze), duration of pelvic floor lift (in seconds), valsalva angle (minimum angle), number of pelvic floor lift/relax repetitions in 15 seconds. All of these data will be reported as continuous.
- **Brink Score:** Scoring will be conducted as medically directed. All of the ratings will be summed and reported as a continuous variable.

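### SAP 3.5 compares continuous week-8 measures by arm alone; adding each measure's own pre-randomisation value would narrow the confidence intervals at almost no cost

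*SAP*

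**What the plan says.** SAP 3.5 gives three methods for continuous variables: Student's t-test when normally distributed, the Wilcoxon rank-sum test when not, and a regression for the effect size: "Linear regression will be used to calculate difference in means and 95% CI to assess the relationship between the intervention and all continuous variables". No covariate is named for the regression, and the two tests cannot take one. The section's only adjustment sentence is optional, depends on baseline differences being seen, and is confined to log-binomial models for binary outcomes.

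SAP 3.4 fixes six measures as continuous. Of the five PFDx measures it says "All of these data will be reported as continuous", and of the Brink score "All of the ratings will be summed and reported as a continuous variable". PFDI, PFIQ and SESPPFE may be continuous or categorised, and WHODAS has two scoring options. The baseline angle in the PFDx list is the resting angle, which is itself an outcome and not a covariate. SAP 3.1 uses baseline results descriptively only.

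The baseline data are planned. Protocol 8.1 provides for "pelvic floor muscle testing using the PFDx device at in-office visits at baseline, 4 weeks and 8- weeks". At the baseline visit, "the randomization will occur following the above surveys and evaluations". Under Protocol 4 and 8.1 the Brink score is taken at baseline, or at screening if that was less than 3 months earlier, and again at week 8.

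**The concern.** In a randomised comparison of a week-8 measurement, part of the spread between women was already there at baseline. When that baseline value has been recorded, leaving it out of the model keeps this spread in the error term. The estimate stays valid but its interval is wider than it need be. With 30 women per arm (SAP 2) such a loss is worth avoiding, because in a pilot the interval estimates are among the most useful results.

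The measures are not incidental. Protocol 7.1 includes the hypothesis that the device "leads to more significant improvements in pelvic floor muscle performance than a home PFME program", and the flow chart in Protocol 4 uses PFDx to assess that performance. The plan also provides no adjustment route for a PFDx measure that happens to be imbalanced, since its adjustment sentence covers log-binomial models only.

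**Working it through.** **The plan's own figure.** Protocol 10.1.1 gives 93 per arm for 30% versus 50% success on PGI-I, two-sided 0.05, power 0.8:

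n = [1.96·√(2·0.40·0.60) + 0.842·√(0.30·0.70 + 0.50·0.50)]² / 0.20² = (1.358 + 0.571)² / 0.04 ≈ 93.

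This reproduces. In total, 186 / 0.85 = 219, close to the stated 225. The calculation is for a binary outcome only; the documents contain none for a continuous measure.

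**Inputs for the continuous measures**
- From the documents: 30 per arm (SAP 2); two-sided 0.05 (SAP 3.5); about 15% attrition (Protocol 10.1.1), so 30 × 0.85 = 25.5, taken as 25 per arm.
- Assumed: correlation r between baseline and week 8 of 0.3, 0.5 or 0.7; an illustrative difference of 0.5 SD. The documents give no SD, correlation or effect size for these measures.

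**Formulae**, in SD units of the week-8 measure
- Arm only: SE = √(2/n). At n = 30 this is 0.258.
- Arm plus own baseline (ANCOVA): SE = √(2/n)·√(1 − r²). At n = 30 this is 0.246, 0.224 and 0.184.
- Ratio √(1 − r²) = 0.954, 0.866 and 0.714, so intervals are 5%, 13% and 29% narrower before paying for the extra term.
- Equivalent arm-only size, 30/(1 − r²): 33, 40 and 59 per arm.

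**Simulation**, 20,000 trials per cell with normal outcomes and complete data, which does charge for the extra term:

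| | Arm only | r = 0.3 | r = 0.5 | r = 0.7 |
|---|---|---|---|---|
| Variance ratio, 30 per arm | 1 | 0.93 | 0.76 | 0.52 |
| CI half-width (SD), 30 per arm | 0.51 | 0.50 | 0.45 | 0.37 |
| CI narrower by, 30 per arm | – | 4% | 12% | 28% |
| Power for 0.5 SD, 30 per arm | 48% | 51% | 58% | 75% |
| CI half-width (SD), 25 per arm | 0.57 | 0.55 | 0.50 | 0.41 |
| Power for 0.5 SD, 25 per arm | 41% | 44% | 51% | 67% |

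With no true effect, rejection was 4.8–5.1% for the t-test and 4.8–5.0% for ANCOVA, so both hold their level.

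**Change from baseline is not equivalent.** Its variance relative to the arm-only comparison is 2(1 − r) = 1.40, 1.00 and 0.60. It is worse than arm-only at r = 0.3, no better at 0.5, and behind ANCOVA throughout.

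**Skewed scores.** These were simulated as 10·exp(0.8z) − 3 clipped to 0–100, with a 0.5 SD effect on the latent scale and 6,000 trials per cell:

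| Power | r = 0.3 | r = 0.5 | r = 0.7 |
|---|---|---|---|
| Rank-sum (planned), 30 per arm | 45% | 46% | 44% |
| ANCOVA on the raw score, 30 per arm | 39% | 44% | 57% |
| Rank ANCOVA, 30 per arm | 48% | 55% | 70% |
| Rank-sum (planned), 25 per arm | 39% | 38% | 39% |
| ANCOVA on the raw score, 25 per arm | 34% | 37% | 49% |
| Rank ANCOVA, 25 per arm | 41% | 47% | 61% |

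A repeat run put raw-score ANCOVA at 41% for r = 0.3 and 30 per arm, still below rank-sum. Null rejection was 4.0–4.9% for raw-score ANCOVA and 4.9–5.3% for rank ANCOVA. For such scores the raw-score p-value can therefore lose power at low correlation, while rank ANCOVA did better than rank-sum at every correlation tried.

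**The case against.** The strongest reply is that nothing here is an error. The planned tests are valid, and the SAP covers a study stopped early and analysed as a pilot. Its objectives are feasibility, technical issues and compliance (SAP 1), and both outcomes it calls primary are binary (SAP 3.4). SAP 3.5 closes by asking for caution. All of this stands, and it makes the point an improvement rather than a correction.

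The size of the gain is also assumed. At r = 0.3 it is a 4% narrower interval and three points of power. For Brink, a screening examination up to 3 months before baseline could lower the correlation. Brink is also missing from the baseline list in SAP 3.1 and from the opening week-8 list in SAP 3.4, although the protocol collects it at both times. These reservations limit the benefit but give no reason to omit the term.

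The objection that raw-score ANCOVA can lose power on skewed scores is correct, and it shapes the fix.

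A reader might infer that the trial falls short on a protocol primary objective because only 60 of 225 women were enrolled. The documents do not support this: 225 was derived for PGI-I alone, and the SAP does not carry the muscle-performance objective forward. Nor does the SAP forbid adjustment. SAP 4.2 allows further analyses at discretion, though that is not a specified adjustment.

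**Conclusion.** The point holds as a nearly free improvement. For the five PFDx measures and the Brink score, and for other scores if analysed as continuous, the planned intervals are wider than the data allow. With 30 per arm and r of 0.3, 0.5 or 0.7, the avoidable excess is worth a 4%, 12% or 28% narrower interval. The correlation, the 0.5 SD difference, the normal outcomes and complete data are assumptions. With 25 per arm the proportional gain is about the same.

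Two stronger readings should be resisted. One is that the unadjusted comparison is biased or inflates type I error. It does neither: allocation is randomised and the simulated error rate is nominal. The other is that the point undermines the efficacy results. It does not reach the PGI-I outcome, which has no meaningful baseline counterpart, and it makes no claim about the risk ratios.

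**What to change.** In SAP 3.5, for each outcome analysed as continuous and measured at baseline:

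- Fit the planned linear regression with arm plus that outcome's own pre-randomisation value, and take the estimate and 95% CI from it, whether or not baseline imbalance is seen.
- For normally distributed measures, take the p-value from the same model.
- For measures the SAP would send to the rank-sum test, take the main p-value from a rank ANCOVA (week-8 ranks regressed on arm and baseline ranks) in place of the rank-sum test.
- Do not substitute a plain change-from-baseline comparison.

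The cost is a few lines of SAP text, one degree of freedom per model, and the loss of any woman without a baseline value. The SAP was written after the study had ended early, so this is weaker than true pre-specification. The own-baseline rule does at least leave no covariate to choose. No new data are needed.
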